## AMENDMENT HISTORY

### Amendment 2

The primary purpose of this amendment is to pre-specify a first-step analysis and make adjustments to the planned statistical methodology.

Description of Change	Brief Rationale	Section(s)
Study enrollment has been closed.	Based on assessment that the study is adequately powered with current enrollment	Section 6.1 Study Description and Duration
A primary efficacy analysis will be conducted as a first-step analysis using the first 816 patients enrolled in the study. This analysis represents the final analysis of the primary endpoint and is not considered an interim analysis.	To pre-specify the first-step analysis and other planned statistical analyses of the study	Section 6.3 Planned Interim Analysis Section 8.7 Blinding Section 11 Statistical Plan Section 11.2 Justification of Sample Size Section 11.4.9 Timing of Statistical Analyses [new] Section 11.5 Interim Analysis
The following additional changes have been made with respect to the statistical design of the study: 
 
• Virologic endpoints assessing changes in cycle threshold (Ct) are now exploratory; these were previously planned as secondary analyses
 
• Exploratory endpoints have been added to assess the proportion of patients with <math>\geq 1</math> COVID-19-related hospitalization/all-cause death or <math>\geq 1</math> COVID-19-related hospitalization/emergency room visit/all-cause death
 
• Exploratory endpoints assessing the cumulative incidence of various COVID-19-related medically-attended visits have been removed; corresponding proportion-based endpoints have been retained
 
• Associated details (eg, study variables, primary and secondary efficacy analyses) have been updated to reflect the planned statistical analysis
 
	To clarify the planned study analyses	Section 4.2 Secondary Endpoints Section 4.3 Exploratory Endpoints Section 5.1 Demographic and Baseline Characteristics Figure 1 Study Flow Diagram Section 11.3.1 Efficacy Analysis Sets Section 11.3.1.1 The Seronegative Modified Full Analysis Set [new] Section 11.3.1.2 Per Protocol Set [new] Section 11.4.3.1 Primary Efficacy Analysis Section 11.4.3.2 Secondary Efficacy Analysis Section 11.4.4 Control of Multiplicity Section 11.4.5.1 Adverse Events
Clarified in the schedule of events that study visits are not required solely to collect continuously-monitored assessments, if no other assessments are planned on that day.	To ensure operational clarity and avoid unnecessary study visits	Table 1 Schedule of Events Section 9.1.1 Footnotes for the Schedule of Events Table, #6
Clarified that for patients with symptoms of COVID-19 at screening, the severity of symptoms will be recorded and graded in the eCRF using the current version of the NCI-CTCAE v5.0.	To capture additional clinically-relevant information regarding COVID-19 illness	Table 1 Schedule of Events Section 9.1.1 Footnotes for the Schedule of Events Table, #12 Section 9.2.1.4 Medical History

Description of Change	Brief Rationale	Section(s)
Clarified that during each indicated collection visit (as provided in the schedule of events), all previously unrecorded COVID-19-related medically-attended visits and details will be recorded, beginning from the day of dosing up to and including the day of collection.	To ensure appropriate capturing of clinically-relevant information	Section 9.2.10.3 COVID-19-Related Medically-Attended Visit Details
The risk-benefit section has been updated to reflect the current Investigator's Brochure (edition 5). This update includes the addition of hypersensitivity reactions (including infusion-related reactions and injection site reactions) as an important identified risk.	To provide current information regarding the potential risks and benefits of REGN10933 + REGN10987	Section 3.3 Risk-Benefit
Provided updated CDC guidance regarding COVID-19 vaccination.	To ensure accurate and current medical information	Section 7.2.1 Inclusion Criteria, #7 Section 8.10.1 Prohibited and Permitted Medications
In light of the increasing number of therapeutic and preventative COVID-19 agents approved or conditionally authorized, reference to individual agents has been removed. References to FDA and EMA have been provided as a general resource for currently-available agents.	To ensure current, accurate, and consistent information	Section 1.6 A Randomized, Placebo-Controlled Study of Anti-SARS-CoV-2 S Protein Monoclonal Antibodies in Outpatients with SARS-CoV-2 Infection
Minor administrative changes, updates to background information, and other minor typographical corrections were made.	To ensure current, accurate, and consistent information	Throughout the document

**Amendment 1**

The primary purpose of this amendment is to modify the study design per health authority request.

Description of Change	Brief Rationale	Section(s)

In addition to current safety information collection, the following additional information will be collected:
 
 
• All treatment-emergent adverse events (TEAEs) through day 29
 
• TEAEs that led to a hospitalization or emergency room visit, regardless of relatedness to COVID-19, through day 169
 
• Grade <math>\geq 3</math> TEAEs through day 169
 
• All serious adverse events (SAEs) through day 169
 
• Any clinically-significant laboratory findings
 
 
Exploratory endpoints have been added and/or modified to accommodate the additional collection of safety information.
	
Per health authority request, for more comprehensive analysis of safety profile and to further assess patient safety by extending the follow-up period to cover approximately 5 half-lives of REGN10933 + REGN10987
	
Section 2.3 Exploratory Objectives            Section 3.2.1 Rationale for Study Design            Section 4.3 Exploratory Endpoints            Section 5.3 Safety Variables            Section 6.1 Study Description and Duration            Table 1 Schedule of Events            Section 9.1.1 Footnotes for the Schedule of Events Table, #5, 8            Section 9.2.4.2 Adverse Event Monitoring            Section 9.2.5 Post-Day 22 Follow-up by Phone            Section 9.2.7 Laboratory Testing            Section 10.1.1 General Guidelines            Section 10.1.3 Events that Require Expedited Reporting to Sponsor            Section 11.4.5.1 Adverse Events

Details of COVID-19-related medically-attended visits will be collected through day 169. Collection previously ended at day 29.
	
For more comprehensive exploratory assessment of clinical outcomes
	
Table 1 Schedule of Events


Blood samples for drug concentration and immunogenicity assessments will be collected on day 120.
 
Anti-drug antibody (ADA) and neutralizing antibody (NAb)-related objectives, endpoints, and analyses have been added accordingly.
	
For comprehensive analysis of drug concentrations and immunogenicity of REGN10933 and REGN10987 over time, at different dose levels and routes of administration
	
Section 2.2 Secondary Objectives            Section 3.3 Risk-Benefit            Section 4.2 Secondary Endpoints            Section 5.5 Immunogenicity Variables [new]            Section 6.1 Study Description and Duration            Table 1 Schedule of Events            Section 9.1.1 Footnotes for the Schedule of Events Table, #10            Section 11.3.4 Immunogenicity Analysis Set [new]            Section 9.2.8 Drug Concentration Measurements and Samples            Section 9.2.9 Immunogenicity Measurements and Samples [new]            Section 11.4.8 Analysis of Immunogenicity Data [new]            Section 11.4.8.1 Analysis of Neutralizing Antibody Data [new]

The following study visit modifications have been made:
 
 
• Phone visits were added at day 90 and day 169
 
• An in-person visit was added at day 120
 
	
To accommodate the additional safety, drug concentration, and immunogenicity assessments
	
Section 3.3 Risk-Benefit            Section 6.1 Study Description and Duration            Figure 1 Study Flow Diagram            Table 1 Schedule of Events

Description of Change	Brief Rationale	Section(s)

 
The study duration has been extended from 61 days to 170 days
 
		Section 9.1.2 Early Termination from the Study
Grade $\geq 3$ injection-site reactions (ISRs) will be reported as AESIs. Grade 2 ISRs will no longer be considered AESIs.	To collect the most medically-relevant AESIs	Section 8.5.2 Injection Reactions Table 1 Schedule of Events Section 10.1.1 General Guidelines Section 10.1.3 Events that Require Expedited Reporting to Sponsor

The following changes and clarifications were made with respect to assessment of women of childbearing potential (WOCBP) and women who are pregnant:
 
 
In addition to the standard collection of pregnancy outcome information, for newborn infants of patients who were treated in the study and were pregnant at randomization or became pregnant at any time while in the study, the incidence and outcome of any SARS-CoV-2 infection [in the newborn] will be collected on day 120 and day 169
 
Pregnancy testing at screening must be performed in all WOCBP, regardless of pregnancy status
 
Pregnancy or breastfeeding status at screening must be collected as medical history, if applicable
 
A paper pregnancy report form must be completed for each patient who becomes pregnant or is pregnant at the signing of consent.
 
	To ensure accurate information is collected regarding pregnancy; per health authority request, to assess any treatment effects on vertical transmission of SARS-CoV-2	Table 1 Schedule of Events Section 9.1.1 Footnotes for the Schedule of Events Table, #7 Section 9.2.1.4 Medical History Section 9.2.5 Post-Day 22 Follow-up by Phone Section 10.1.3 Events that Require Expedited Reporting to Sponsor Section 9.2.6 Pregnancy Test for Women of Childbearing Potential

The following modifications have been made, and information provided, with respect to SARS-CoV-2 vaccination:
 
 
Patients will be excluded based on prior use, current use, or planned use (within time period given per CDC guidance but no sooner than 22 days after study drug administration) of any authorized or approved vaccine for SARS-CoV-2.
 
Patients will be excluded if they have any prior participation, current participation, or any future plans to participate in a clinical research study evaluating any authorized, approved, or investigational vaccine for SARS-CoV-2
 
SARS-CoV-2 vaccines will be captured as targeted concomitant medication.
 
 
In addition, current CDC guidance related to vaccination has been provided for reference. This guidance recommends deferral of SARS-CoV-2 vaccination for at least 90 days after administration of passive antibody treatment (eg, REGN10933+REGN10987) (CDC, 2020)
	Per current CDC recommendations on SARS-CoV-2 vaccination	Section 7.2.2 Exclusion Criteria, #7, #11 [new] Section 8.10.1 Prohibited and Permitted Medications 9.2.4.3 Record Targeted Concomitant Medications
Clarified that viral variants suspected to confer decreased susceptibility to REGN10933 and/or	Per health authority request	Section 9.2.10.1 Virology

Description of Change	Brief Rationale	Section(s)
REGN10987 will be evaluated in nonclinical work separate from this protocol.		
Clarified that for the screening SARS-CoV-2 diagnostic test, the sample must be collected $\leq 72$ hours of randomization. Samples are not valid for screening if collected $>72$ hours from randomization, even if the test is performed, or results reported, within the 72-hour window.	To ensure appropriate screening for SARS-CoV-2 infection	Section 7.2.1 Inclusion Criteria, #2
Removed language stating that if diagnostic SARS-CoV-2 testing was performed outside of the allowed window, a new test is required for study inclusion. Language had previously been retained in error. Per study exclusion criteria, patients will be excluded if they have a positive SARS-CoV-2 antigen or molecular diagnostic test from a sample collected $>72$ hours prior to randomization	To ensure accurate information	Section 9.2.1.2 Diagnostic Test for SARS-CoV-2
Members of the clinical site study team and/or their immediate family will be now considered a study exclusion criterion.	To avoid the appearance of conflict of interest or coercion, and to ensure integrity of study data	Section 7.2.2 Exclusion Criteria, #12 [new]
The schedule of events was corrected to reflect treatment-emergent grade $\geq 2$ hypersensitivity reactions will be assessed through day 29. Previous schedule incorrectly stated that assessment would occur through day 22.	To ensure accurate information	Table 1 Schedule of Events
Updates to background information and other minor updates were made.	To ensure current, accurate, and consistent information	Throughout the document

**LIST OF ABBREVIATIONS AND DEFINITIONS OF TERMS**

AAS	Anti-drug antibody analysis set
ADA	Anti-drug antibody
AE	Adverse event
AESI	Adverse event of special interest
CRF	Case report form (electronic or paper)
CRO	Contract research organization
Ct	Cycle Threshold
CTCAE	Common Terminology Criteria for Adverse Events
EDC	Electronic data capture
EOS	End of study
ET	Early termination
FDA	Food and Drug Administration
GCP	Good Clinical Practice
ICF	Informed consent form
ICH	International Council for Harmonisation
IRB	Institutional Review Board
IV	Intravenous
MAV	Medically-attended visit
mFAS	Modified full analysis set
NAb	Neutralizing antibody
NCI-CTCAE	National Cancer Institute-Common Terminology Criteria for Adverse Events
PK	Pharmacokinetic
PPE	Personal protective equipment
RBQM	Risk-Based Quality Monitoring
RT-qPCR	Quantitative reverse transcription polymerase chain reaction
SAE	Serious adverse event
SAF	Safety analysis set
SAP	Statistical analysis plan
SAS	Statistical Analysis System
SC	Subcutaneous
SOC	System organ class
SUSAR	Suspected unexpected serious adverse reaction
TEAE	Treatment-emergent adverse event
TWA	Time weighted average

## CLINICAL STUDY PROTOCOL SYNOPSIS

Title	A Phase 2 Study to Assess the Virologic Efficacy of REGN10933+REGN10987 Across Different Dose Regimens in Outpatients with SARS-CoV-2 Infection
Site Locations	The study will be conducted in approximately 80 sites in the United States.
Principal Investigator	To be determined
Objectives	
Primary	
 
To assess the virologic efficacy of REGN10933+REGN10987 across different intravenous and subcutaneous doses compared to placebo
 

Secondary	
 
To evaluate additional indicators of virologic efficacy of REGN10933+REGN10987 compared to placebo
 
To evaluate the safety and tolerability of REGN10933+REGN10987 compared to placebo
 
To assess the concentrations of REGN10933 and REGN10987 in serum over time
 
To assess the immunogenicity of REGN10933 and REGN10987
 

Study Design	
Note: as of protocol amendment 2, study enrollment is closed.
 
This is a randomized, double-blind, placebo-controlled, parallel group study to assess the dose response profile of single intravenous (IV) or single subcutaneous (SC) doses of REGN10933+REGN10987 in outpatients with SARS-CoV-2 infection.
 
Eligible patients will be randomized to receive a single dose of REGN10933+REGN10987 or placebo by IV or SC route. On the day of dosing, patients will have NP swabs taken for SARS-CoV-2 RT-qPCR testing and blood drawn for safety, drug concentration, immunogenicity, and serologic analyses. After study drug administration, patients will have a post-dose blood collection (either at the end of intravenous infusion or at least 1 hour after subcutaneous administration). Patients will be monitored for at least 1 hour after study drug administration and then released from the study site, if medically appropriate.
 
Information related to safety and COVID-19-related medically-attended visits will be recorded during planned study visits. Patients will also be asked to notify study personnel as soon as possible about any medically-attended visits. Note that the TEAEs that will be collected during the study will differ according to different periods of the study schedule. Refer to the safety reporting section in the protocol for more information on reporting of TEAEs and treatment-emergent laboratory abnormalities.
 
Patients will have NP swabs and blood samples collected every other day for the first week of the study. Additional NP swab samples will be collected once-weekly for 2 more weeks to assess potential persistence of viral load. A phone visit will occur during the fourth week for collection of safety information.
 
After the first month, patients will have visits approximately once-monthly for 4 additional months. The penultimate visit will be in-person to collect blood samples for drug concentration and immunogenicity. The final visit (EOS) will be a phone call.

Study Duration	The duration of the study is 170 days for each patient.
End of Study Definition	The end of study is defined as the date when the last living patient completes the last study visit, withdraws from the study, or is lost to follow-up (ie, the study patient can no longer be contacted by the investigator).
Population	
Sample Size	Up to approximately 1400 patients will be enrolled.
Target Population	This study will enroll adult, non-hospitalized patients who have a positive diagnostic test for SARS-CoV-2.

**Inclusion criteria:** A patient must meet the following criteria to be eligible for inclusion in the study. Other inclusion criteria also apply and are described in the main text.

- Is male or female  $\geq 18$  years of age (or country's legal age of adulthood) at randomization  
*Note: upper age limit may apply; refer to other inclusion criteria.*
- Has SARS-CoV-2-positive diagnostic test from a sample collected  $\leq 72$  hours prior to randomization, using a validated SARS-CoV-2 antigen, RT-PCR, or other molecular diagnostic assay and an appropriate sample such as nasopharyngeal (NP), nasal, oropharyngeal (OP), or saliva  
*Note: Historical record of positive result is acceptable, as long as the sample was collected  $\leq 72$  hours prior to randomization.*
- **Low-risk symptomatic patient:** Has symptoms consistent with COVID-19 (as determined by the investigator) with onset  $\leq 7$  days before randomization, and **meets all of the following 8 criteria:**
  - Age  $\leq 50$
  - No obesity, with obesity defined as BMI  $\geq 30$  kg/m^2
  - Does not have cardiovascular disease or hypertension
  - Does not have chronic lung disease or asthma
  - Does not have type 1 or type 2 diabetes mellitus
  - Does not have chronic kidney disease, with or without dialysis
  - Does not have chronic liver disease
  - Is not pregnant

**or**

*Asymptomatic patient:* Has had no symptoms consistent with COVID-19 (as determined by the investigator) occurring at any time  $< 2$  months prior to randomization

**Exclusion criteria:** A patient who meets any of the following criteria will be excluded from the study. Other exclusion criteria also apply and are described in the main text.

- Was admitted to a hospital for COVID-19 prior to randomization, or is hospitalized (inpatient) for any reason at randomization
- Has a known positive SARS-CoV-2 serologic test
- Has a positive SARS-CoV-2 antigen or molecular diagnostic test from a sample collected  $> 72$  hours prior to randomization
- Is immunosuppressed, based on investigator's assessment  
*Note: examples include cancer treatment, bone marrow or organ transplantation, immune deficiencies, HIV (if poorly controlled or evidence of AIDS), sickle cell anemia, thalassemia, and prolonged use of immune-weakening medications.*
- Has participated, or is participating, in a clinical research study evaluating COVID-19 convalescent plasma, mAbs against SARS-CoV-2, or intravenous immunoglobulin (IVIG) within 3 months or within 5 half-lives of the investigational product (whichever is longer) prior to the screening visit
- Prior, current, or planned future use of any of the following treatments: COVID-19 convalescent plasma, mAbs against SARS-CoV-2 (eg, bamlanivimab), IVIG (any indication), systemic corticosteroids (any indication), or COVID-19 treatments (authorized, approved, or investigational)  
*Note: prior use is defined as the past 30 days or within than 5 half-lives of the investigational product (whichever is longer) from screening.*
- Prior use (prior to randomization), current use (at randomization), or planned use (within time period given per CDC guidance but no sooner than 22 days of study drug administration) of any authorized or approved vaccine for COVID-19

*Note: As of 02 March 2021, CDC guidance recommends deferral of SARS-CoV-2 vaccination for at least 90 days after administration of passive antibody therapy. Additional information can be found in the main text.*

- Has participated, is participating, or plans to participate in a clinical research study evaluating any authorized, approved, or investigational vaccine for SARS-CoV-2

---

### Treatments

**IV Single Dose** Co-administered REGN10933+REGN10987 combination therapy intravenous (IV) single dose:

- 2400 mg (1200 mg per monoclonal antibody [mAb])
- 1200 mg (600 mg per mAb)
- 600 mg (300 mg per mAb)
- 300 mg (150 mg per mAb)
- Placebo IV single dose

**SC Single Dose** Co-administered REGN10933+REGN10987 combination therapy subcutaneous (SC) single dose

- 1200 mg (600 mg per mAb)
  - 600 mg (300 mg per mAb)
  - Placebo SC single dose
- 

### Endpoints

**Primary** Time-weighted average daily change from baseline in viral load ( $\log_{10}$  copies/mL) from day 1 to day 7, as measured by RT-qPCR in NP swab samples, in patients who have a central-lab determined RT-qPCR positive test and are seronegative at baseline

**Secondary**

- Time-weighted average daily change from baseline in viral load ( $\log_{10}$  copies/mL) from day 1 to day 5
- Time-weighted average daily change from baseline in viral load ( $\log_{10}$  copies/mL) in patients with high viral load at baseline ( $>10^4$  copies/mL,  $>10^5$  copies/mL,  $>10^6$  copies/mL,  $>10^7$  copies/mL) from day 1 to day 7
- Time-weighted average daily change from baseline in viral load ( $\log_{10}$  copies/mL) in patients with high viral load at baseline ( $>10^4$  copies/mL,  $>10^5$  copies/mL,  $>10^6$  copies/mL,  $>10^7$  copies/mL) from day 1 to day 5
- Proportion of patients with high viral load ( $>10^4$  copies/mL,  $>10^5$  copies/mL,  $>10^6$  copies/mL,  $>10^7$  copies/mL) at each visit
- Proportion of patients with viral loads below the limit of detection at each visit
- Proportion of patients with viral loads below the lower limit of quantification at each visit
- Change from baseline in viral load ( $\log_{10}$  copies/mL) at each visit, as measured by RT-qPCR in NP samples
- Proportion of patients with treatment-emergent SAEs through day 29
- Proportion of patients with infusion-related reactions (grade  $\geq 2$ ) through day 4
- Proportion of patients with injection-site reactions (grade  $\geq 3$ ) through day 4
- Proportion of patients with hypersensitivity reactions (grade  $\geq 2$ ) through day 29
- Concentrations of REGN10933 and REGN10987 in serum over time
- Immunogenicity as measured by anti-drug antibodies (ADAs) and neutralizing antibodies (NAb) to REGN10933 and REGN10987

---

**Procedures and Assessments** Procedures and assessments will include:

- NP swabs for SARS-CoV-2 RT-qPCR
  - COVID-19-related medically-attended visits
-

- 
- TEAEs, treatment-emergent SAEs, and treatment-emergent AESIs (grade  $\geq 2$  infusion-related reactions, grade  $\geq 3$  injection-site reactions, grade  $\geq 2$  hypersensitivity reactions, and any TEAE that led to a hospitalization or emergency room visit, regardless of whether the visit is related to COVID-19)
  - Targeted concomitant medications, safety labs, vital signs, and pregnancy status
- 

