#### **11.3.2. Safety Analysis Set**

The safety analysis set (SAF) includes all randomized patients who received any study drug; it is based on the treatment received (as treated). Determination of “as treated” will be based on the actual study drug received on day 1. Demographic and baseline characteristics, treatment compliance/administration and all clinical safety variables will be analyzed using the SAF.

In the SAF population, the placebo arms for the IV and SC routes of administration will be summarized separately.

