##### Analysis

All adverse events reported in this study will be coded using the currently available version of the Medical Dictionary for Regulatory Activities (MedDRA®). Coding will be to lowest level terms. The preferred term (PT), and the primary system organ class (SOC) will be listed.

Summaries by treatment group will include the following:

- The number (n) and percentage (%) of patients with at least 1 treatment-emergent AE through day 29 by SOC and PT
- The number (n) and percentage (%) of patients with at least 1 treatment-emergent grade 3 or 4 AE through day 169 by SOC and PT
- The number (n) and percentage (%) of patients with at least 1 treatment-emergent SAE through day 29 by SOC and PT
- The number (n) and percentage (%) of patients with at least 1 infusion-related reaction (grade  $\geq 2$ ), through day 4 by PT
- The number (n) and percentage (%) of patients with at least 1 injection-site reaction (grade  $\geq 3$ ), through day 4 by PT

- The number (n) and percentage (%) of patients with at least 1 hypersensitivity reaction (grade  $\geq 2$ ), through day 29 by PT

Summaries of SAEs and AESIs by treatment group will include:

- The number (n) and percentage (%) of patients with at least 1 event by SOC and PT
- SAEs and AESIs by severity (according to the grading scale outlined in Section 10.2.5), presented by SOC and PT
- SAEs and AESIs by relationship to treatment (related, not related), presented by SOC and PT
- Treatment-emergent SAEs and AESIs

Deaths and other SAEs will be listed and summarized by treatment arm.

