This randomization ratio means ~200 subjects in each arm receiving REGN10933+REGN10987 and ~200 subjects receiving placebo (i.e., 100 with IV and 100 with SC). For the purpose of all

virological and efficacy analyses, the placebo arms from the two routes of administration will be pooled because the route of administration does not alter the pharmacodynamic response of patients receiving placebo. Treatment groups for active doses will not be pooled.

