5.8.1. Adverse Events

Safety data will be summarized in three periods:

1. The pretreatment period, i.e., from signing the ICF to before the study drug administration
2. The 29-day observation period, i.e., from the time of the administration of the study drug to the last follow-up visit.
3. The full observation period, i.e., from the time of the administration of the study drug to the last follow-up visit.

For patients that are vaccinated for SARS-CoV-2, only the safety data before vaccination will be used in the primary safety analysis. A secondary safety analysis will use all data collected.

Analysis

All SAEs and AESIs reported in this study will be coded using the currently available version of the Medical Dictionary for Regulatory Activities (MedDRA[®]). Coding will be to lowest level terms. The preferred term (PT), and the primary system organ class (SOC) will be listed.

Summaries by treatment group will include the following:

- The number (n) and percentage (%) of patients with at least 1 treatment-emergent adverse events (AEs) through day 29 by system organ class and PT
- The number (n) and percentage (%) of patients with at least 1 treatment-emergent serious adverse events (SAEs) through day 29 by system organ class and PT
- The number (n) and percentage (%) of patients with at least 1 infusion-related reactions (grade ≥ 2), through day 4 by PT
- The number (n) and percentage (%) of patients with at least 1 injection-site reaction (grade ≥ 3), through day 4 by PT
- The number (n) and percentage (%) of patients with at least 1 hypersensitivity reactions (grade ≥ 2), through day 29 by PT
- Any TEAE that led to a hospitalization or emergency room visit, regardless of whether the visit is related to COVID-19, up to day 169
- Treatment-emergent AEs (grade 3 or 4) from day 30 to day 169
- Treatment-emergent SAEs, up to day 169

Summaries of SAEs and AESIs by treatment group will include:

- The number (n) and percentage (%) of patients with at least 1 event by SOC and PT
- SAEs and AESIs by severity (according to the grading scale described in the protocol), presented by SOC and PT

- SAEs and AESIs by relationship to treatment (related, not related), presented by SOC and PT
- Treatment-emergent SAEs and AESIs
- The number (n) and percentage (%) of patients with Grade 3 or Grade 4 treatment-emergent adverse events.

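### Safety events not specific to one route are shown only by arm, against a placebo column of about 58 to 100 patients, with no combined comparison or interval

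*Protocol*

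**What the plan says.** The secondary safety objective is "To evaluate the safety and tolerability of REGN10933+REGN10987 compared to placebo" (Protocol synopsis and 2.2; SAP 1.2.2). Protocol 4.2 and SAP 1.2.4 list four secondary safety endpoints. Two belong to one route: infusion-related and injection-site reactions, both through day 4. The other two are collected under both routes: "Proportion of patients with treatment-emergent SAEs through day 29", and grade ≥2 hypersensitivity through day 29.

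Protocol 11.3.2 sets the display rule for all clinical safety variables: "In the SAF population, the placebo arms for the IV and SC routes of administration will be summarized separately". SAP 3.3 repeats it. Neither makes an exception by type of event.

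The tables follow the same unit. SAP 5.8.1 has "Summaries by treatment group will include the following" and "Summaries of SAEs and AESIs by treatment group will include", and Protocol 11.4.5.1 adds "Deaths and other SAEs will be listed and summarized by treatment arm". Neither section names an all-placebo column, an all-active column, a risk difference or a confidence interval. Overall columns are planned for demographics, medical history and prior medications (Protocol 11.4.2; SAP 5.1 to 5.3), but not for adverse events.

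For virologic and efficacy analyses the two placebo arms are pooled, with a reason given (Protocol 11.2; SAP 2.1). No reason is given for keeping them apart for SAEs, deaths or severe TEAEs.

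**The concern.** Keeping placebo apart by route is right for infusion-related and injection-site reactions, whose definitions in Protocol 10.2.4 refer to the infusion or the injection. SAEs, deaths, grade 3-4 TEAEs and TEAEs leading to hospitalisation or an ER visit have one definition for both routes, yet the same split applies to them. Each placebo arm gets 1 of 14 allocation units, so the control column for a rare event is half the size of a dose arm and will often contain no event.

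The objective speaks of a comparison with placebo, but the plan never forms one for these events: the reader is given eight columns of counts and percentages. Any combined estimate would have to be built after unblinding, with the method chosen by whoever builds it. Adding up columns is not neutral either, because active-to-placebo allocation is 8:1 for IV and 4:1 for SC.

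**Working it through.** **Inputs**
- Allocation 2:2:2:2:1 for IV (four doses, placebo) and 2:2:1 for SC (two doses, placebo), 14 units in all (Protocol 8.6; SAP 2.1).
- Upper N: about 1400 (Protocol 7.1). Lower N: 816, the first-step set (Protocol 11.4.9). Final enrolment is not stated. The words used for the first-step set imply that more than 816 were enrolled, so 816 is a lower bound. The safety set also requires dosing, so actual columns may be slightly below the allocation figures.
- Event risk: not in the documents. Assumed 1% in both groups, with 0.5% to 3% as the range.

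**The plan's own figure first.** SAP 2.1 states "This randomization ratio means ~200 subjects in each arm receiving REGN10933+REGN10987", with 100 placebo patients per route. Arm size = N × ratio / 14: 1400 × 2/14 = 200 and 1400 × 1/14 = 100. Both reproduce.

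**Column sizes**

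| | N=816 | N=1400 |
|---|---|---|
| One placebo arm (1/14) | 58.3 | 100 |
| Both placebo arms (2/14) | 116.6 | 200 |
| One active arm (2/14) | 116.6 | 200 |
| All IV active (8/14) | 466 | 800 |
| All SC active (4/14) | 233 | 400 |
| All active (12/14) | 699 | 1200 |

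**Half-width of a 95% interval.** With u = N/14 and common risk p, half-width = 1.96 × √[p(1−p) × k/u], where k depends on the comparison:
- one dose versus own-route placebo: k = 1/2 + 1 = 1.5
- one dose versus both placebos: k = 1/2 + 1/2 = 1
- all active versus placebo, stratified by route: IV stratum 1/8 + 1 = 9/8, SC stratum 1/4 + 1 = 5/4, combined k = 1/(8/9 + 4/5) = 0.592. Under a common risk the Mantel-Haenszel weights equal the inverse-variance weights, so either gives this value.

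| Half-width, percentage points, p = 1% | N=816 | N=1400 |
|---|---|---|
| One dose vs own-route placebo | 3.13 | 2.39 |
| One dose vs both placebos | 2.55 | 1.95 |
| All active vs placebo, route-stratified | 1.97 | 1.50 |

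The ratios do not depend on p: √(1/1.5) = 0.816, which is 18% narrower, and √(0.592/1.5) = 0.628, which is 37% narrower. For p from 0.5% to 3%, the three half-widths run 2.2 to 5.4, 1.8 to 4.4 and 1.4 to 3.4 points at N=816, and 1.7 to 4.1, 1.4 to 3.3 and 1.1 to 2.6 at N=1400.

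These are Wald half-widths. With 0.6 to 1.0 expected events per placebo arm they are poor as intervals, and serve here only to compare the displays. The next figures do not rely on them.

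**Chance of an empty placebo column**, (1−p)^n at p = 1%: 56% (n=58) or 37% (n=100) for one arm; 31% or 13% for both arms together.

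**One-sided 95% upper bound after zero events**, 1 − 0.05^(1/n): 5.0% or 3.0% for one placebo arm; 2.5% or 1.5% for both; 0.43% or 0.25% for all active.

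**What the combined comparison still cannot do.** Power of a two-sided 5% Fisher test, all active versus all placebo, unstratified, with 1% on placebo (N=816 rounded to 58 per unit: 116 versus 696; N=1400: 200 versus 1200):

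| Risk on active | N=816 | N=1400 |
|---|---|---|
| 2% | 0.4% | 8% |
| 3% | 9% | 29% |
| 5% | 53% | 84% |

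No safety test is planned. These figures only show how large an excess would have to be to stand out.

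**The case against.** The strongest reply is that this is a dose-ranging study and the tables suit it. A reader might infer from the objective that a comparison of the drug as a whole is required. The text does not say so: the virologic objective in Protocol 2.2 uses the same form of words and is analysed dose by dose, while Protocol 3.2.1 speaks of safety at different single-dose regimens and treats SC administration as an additional aim. That stands. The by-dose tables are a fair reading of the objective, and a combined comparison supplements them.

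A reader might also count hypersensitivity among the route-neutral events, because one definition covers both routes through day 29. Protocol 3.3, 8.5.1 and 8.5.2 tie it partly to infusion and injection reactions, so it does not belong with SAEs and deaths. SAEs and grade 3-4 TEAEs can also include a few administration reactions, which is a reason to stratify by route instead of pooling crudely.

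A third tempting reading is that splitting placebo costs 37% in precision. It costs about 18% for a single dose. The rest comes from combining six active regimens, which changes the question.

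It can also be said that nothing is lost: safety is descriptive, every arm's count is shown, SAEs are listed, and wording of the will-include kind does not forbid further columns. That is true of the data, but it leaves the method of combination to be chosen after unblinding. The statements that active doses are not pooled concern the efficacy and per-protocol sets, so they do not rule out a combined safety column. The composites of COVID-19-related hospitalisation, ER visit and all-cause death do use pooled placebo, but only in the Seronegative mFAS (SAP 4.5.3) and not for SAEs in general.

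**Conclusion.** The point holds as a cheap improvement to the safety display. It is not an error in the plan's figures, which reproduce. For SAEs, deaths, grade 3-4 TEAEs and TEAEs leading to hospitalisation or an ER visit, the split by route has no stated reason, and no comparison or interval is pre-specified.

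The two gains should be kept apart: about 18% for a single dose from pooling placebo, and 37% for the route-stratified drug-level contrast. The column sizes rest on N between 816 and about 1400. The absolute half-widths rest on the assumed risk, while the percentage gains need only a risk common to both groups.

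The documents do not support a claim that the change would reveal a modest safety signal. Total placebo is 117 to 200, and on the assumptions above even a threefold excess would usually be missed. The limit there is the allocation, which the display cannot repair.

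**What to change.** In SAP 5.8.1, with a matching sentence in Protocol 11.3.2 and SAP 3.3:
- Keep all by-dose and by-route columns, and keep infusion-related and injection-site reactions separate by route.
- For SAEs (through day 29 and through day 169), deaths, grade 3-4 TEAEs, and TEAEs leading to hospitalisation or an ER visit, add all-placebo, all-IV-active, all-SC-active and all-active columns.
- For the same events, add a descriptive risk difference of all active versus placebo, stratified by route (for example Mantel-Haenszel), with a 95% interval method suited to rare events, named in advance.
- Present hypersensitivity by route first, with the route-stratified estimate as a supplement.
- State that these estimates are descriptive and that the all-active contrast is a drug-level summary.

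The cost is some SAP wording and a few table columns, with no new data and no change to the primary analysis. The one downside is that a pooled column can mask a dose trend, which is why the by-dose columns stay beside it. The wording should be settled before the first unblinding.
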